PRIMARY FEASIBILITY ENDPOINT:	The proportion of subjects that achieve Acute Procedural Success (APS) defined as the percutaneous endocardial creation of a complete, electrically isolating set of lesions around the ostia of the pulmonary veins (PVI) using the FARAPULSE Endocardial Multi Ablation System during the Index Procedure, as clinically assessed by entrance and/or exit block performed \geq 20 minutes after the last PVI lesion is made.

SECONDARY FEASIBILITY ENDPOINTS:	
1. The proportion of subjects who undergo the protocol-specified 75-Day Remapping Procedure and achieve Chronic Procedural Success (CPS) defined as persistent electrical isolation of all initially ablated pulmonary veins. Chronic Procedural Success will be subdivided by Index Procedure only CPS and Reablated CPS subjects.2. The proportion of attempted subjects that achieve Acute CTI Success, defined as the creation of bi-directional electrical block across the cavotricuspid isthmus using the investigational devices using the FARAPULSE Endocardial Multi Ablation System during the Index Procedure.3. Durability of the CTI and/or other extra-PV lesion set(s), when applicable. Durability is defined as unaltered integrity of each such lesion assessed at the Remapping Procedure.4. The proportion of subjects that achieve Therapeutic Success, defined as freedom from:
a. Post Blanking Period through assessment: occurrence of AF, AFL or AT or ablation for AF/AFL/AT using the study deviceb. At any time: ablation for AF/AFL/AT with a nonstudy device 
Therapeutic Success will be assessed from the end of the 90-day Blanking Period through Months 6 and 12 and will be subdivided by on / off AFDs (Atrial Fibrillation Drugs) post-Blanking Period.

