3.11.3 Blanking Period

The Blanking Period consists of Day 0 (the date of Index Procedure) through and including Day 90.

During the Blanking Period, any recurrence of AF will be documented; however, recurrences of AF, AFL or AT during this time will not be considered Therapeutic Failures.

Subjects may undergo one repeat ablation during the Blanking Period without creating a Therapeutic Failure, following the procedure detailed in the preceding sections. This may occur during the Remap Procedure or at another procedure as clinically indicated.

If a second repeat ablation procedure is performed during this time, or any nonstudy device is used for cardiac ablation, the subjects will be considered a Therapeutic Failure but will remain in the study.

Towards the end of the Blanking Period, any AFD treatment will be discontinued unless the Investigator deems the withdrawal of AFD treatment not to be in the best interests of the patient.

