3.12.3 Pre-Discharge

Prior to hospital discharge the following data will be collected:

- Adverse Events
- Data regarding the use, changes in or discontinuation of anticoagulation, rate control and/or antiarrhythmic medications.
- Cardiac rhythm as determined by a 12-lead ECG
- Occurrence, date, indication and outcome of any cardioversion(s)
- At the investigator's discretion: a post-procedural mediastinal gadolinium-enhanced MRI
- Stroke/TIA assessments

- NIHSS score
- A neurologic examination will be performed and recorded if:
 - If the NIHSS score has increased by 2 or more points
 - If there is a clinical suspicion of stroke or TIA

3.12.4 30-Day Visit

Discharged subjects will return for an office visit 30 days (\pm 7 days) post-ablation treatment. (Any subject who continues to be hospitalized 30 days post-ablation will have their 30-Day Visit assessment performed in-hospital). The following data will be collected at the 30-Day Visit:

- Adverse Events
- Symptoms of recurrent arrhythmia
- Data regarding the use, changes in or discontinuation of anticoagulation, rate control and/or antiarrhythmic medications.
- Cardiac rhythm as determined by a 12-lead ECG at the time of the visit
- Cardioversions, ablations or hospital admissions since last visit
- Heart failure status as assessed by NYHA classification at the time of visit

3.12.5 75-Day Visit and Remapping Procedure

Patients undergoing protocol-specified remapping:

Subjects will undergo the protocol-stipulated remapping procedure at 75 ± 15 days post-Index Procedure as defined in **Section 3.11.2, 75-Day Remap Procedure**.

- A 3D electroanatomical remapping procedure will be performed to assess electrical isolation of the pulmonary veins. Any electrical gaps may be closed at the investigator's discretion using study devices, or if necessary, a commercially approved ablation device (which constitutes a Therapeutic Failure).
- For patients who received extra-PV ablation at index, including those receiving ablation of the CTI, the persistence of nonconductivity in targeted tissue will be evaluated with either pacing maneuvers or electroanatomical mapping.

Procedure-specific data will be collected as follows:

- Procedural times
- Lesion set data
- Device deficiencies and malfunctions

All subjects whether undergoing remapping or not:

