2.3.1. Databases

The Remapping at 75 Days, recurrence and Additional endpoints analysis will be based on the MDT Excel file sent by sponsor, which will contain:

- Received ablation at remap"
- RF/PFA ablation at remap
- Early recurrence of atrial fibrillation (AF)
- AF status
- AF km days"
- Atrial fibrillation/ Atrial flutter / Atrial tachycardia (AF/AFL/AT) status"
- AF/AFL/AT km (days)
- Transtelephonic monitor (TTM) weeks expected
- TTM weeks received
- Number TTM transmissions
- 6-month holter
- 12-month holter
- Radiofrequency (RF) touchup

CONFIDENTIEL / CONFIDENTIAL

Toute reproduction ou distribution, totale ou partielle, de ce document, sans autorisation préalable de ICON PLC est interdite.
Reproduction and distribution of this document, in whole or in part, is strictly forbidden without prior authorization from ICON PLC.

	STATISTICAL ANALYSIS PLAN	FARAPULSE PersAFOne SAP V1.0 PERSAFONE Page 15 /49
---	----------------------------------	--

- Ablation (ABL) >90 days"
- Class I/III antiarrhythmics drug (AAD) >90 days
- Amiodarone
- Direct current cardioversion (DCCV) >90 days
- Arrhythmia-related (AF, AFL, AT) hospitalization

The Excel file sent by the Sponsor will have the same structure (in terms of variables names, labels, formats) for each analysis to ensure the continuity of the programming.

All other analysis will be done on the e-CRF clinical database.

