2.4.6.2. Secondary Feasibility Analysis

The secondary feasibility analyses are:

- The proportion of subjects who undergo the protocol-specified 75-Day Remapping Procedure and achieve Chronic Procedural Success (CPS) defined as persistent electrical isolation of all initially ablated pulmonary veins. Chronic Procedural Success will be subdivided by Index Procedure only CPS and Reablated CPS subjects.
- The proportion of attempted subjects that achieve Acute CTI Success, defined as the creation of bi-directional electrical block across the CTI using the investigational devices.
- Durability of the CTI and/or other extra-PV lesion set(s), when applicable.
Durability is defined as unaltered integrity of each such lesion assessed at the Remapping Procedure.
- The proportion of subjects that achieve Therapeutic Success, defined as freedom from:
 - Post-Blanking Period through assessment: occurrence of AF, AFL or AT, or ablation for AF/AFL/AT using the study device
 - At any time: ablation for AF/AFL/AT with a non-study device
Therapeutic Success will be assessed from the end of the 90 Day Blanking Period through Months 6 and 12 and will be subdivided by on / off AADs (Atrial Fibrillation Drugs) post-Blanking Period.

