- Derived criteria "Durability of Left atrial roof line at remap" will be defined as follows:
IF Left atrial roof line lesion durable ='Yes' in **Follow-up 3D electroanatomical mapping form (RM)** **THEN** Durability of Left atrial roof line at remap = 'Yes'
ELSE IF Left atrial roof line lesion durable ='No' in **Follow-up 3D electroanatomical mapping form (RM)** **THEN** Durability of Left atrial roof line at remap = 'No'
- Derived criteria "Durability of Left atrial Posterior line" will be defined as follows:
IF Left atrial Posterior line lesion durable ='Yes' in **Follow-up 3D electroanatomical mapping form (RM)** **THEN** Durability of Left atrial Posterior line at remap = 'Yes'
ELSE IF Left atrial Posterior line lesion durable ='No' in **Follow-up 3D electroanatomical mapping form (RM)** **THEN** Durability of Left atrial Posterior line at remap = 'No'
- Derived criteria "Therapeutic Success ON/OFF AAD" will be defined as follows:

CONFIDENTIEL / CONFIDENTIAL

Toute reproduction ou distribution, totale ou partielle, de ce document, sans autorisation préalable de ICON PLC est interdite.
Reproduction and distribution of this document, in whole or in part, is strictly forbidden without prior authorization from ICON PLC.

IF "AF/AFL/AT status"= 0 **AND** "RF touchup"= 0 **AND** "ABL >90 days" = 0 **in MDT excel file**
THEN therapeutic success='Yes'
ELSE therapeutic success='No'

- Derived criteria "Therapeutic Success Off ADD" will be defined as follows:
IF Therapeutic success ='Yes' **AND** Class I/III AAD>90days=0 **in MDT excel file** **THEN** therapeutic success Off ADD ='YES'
ELSE IF Therapeutic success ='No' **AND** Class I/III AAD>90days=0 **in MDT excel file** **THEN** **THEN** therapeutic success Off ADD ='NO'
- Derived criteria "Therapeutic Success On ADD" will be defined as follows:
IF Therapeutic success ='Yes' **AND** Class I/III AAD>90days=1 **in MDT excel file** **THEN** therapeutic success On ADD ='No'
Else If Therapeutic success ='No' **AND** Class I/III AAD>90days=1 **in MDT excel file** **THEN** **THEN** therapeutic success On ADD ='No'

Additional endpoints

- Derived criteria "Proportion of all ablated pulmonary veins that are isolated at the Index Procedure using the study device" will be defined as follows:

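### As written, the SAP rule for Therapeutic Success misses non-RF ablation with a non-study device by day 90, and it inherits an unresolved protocol conflict over a second repeat ablation

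*SAP*

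**What the plan says.** **Definition.** SAP 2.4.6.2 gives Therapeutic Success two limbs. The first covers the time after blanking: no AF, AFL or AT, and no study-device ablation. The second is limited neither in time nor by energy source: "At any time: ablation for AF/AFL/AT with a non-study device". Protocol 6.4 has the same second limb: "At any time: ablation for AF/AFL/AT with a nonstudy device". Protocol 3.12.5 applies it at the remap, where gaps may be closed with study devices or, if necessary, with "a commercially approved ablation device (which constitutes a Therapeutic Failure").

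**Blanking rule.** Protocol 3.11.3 sets blanking as day 0 through day 90 and gives one allowance: "Subjects may undergo one repeat ablation during the Blanking Period without creating a Therapeutic Failure". On timing it says: "This may occur during the Remap Procedure or at another procedure as clinically indicated". It then sets the limit: "If a second repeat ablation procedure is performed during this time, or any nonstudy device is used for cardiac ablation", the subject counts as a Therapeutic Failure but stays in the study.

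**Derivation.** SAP 2.5 scores success when AF/AFL/AT status is 0 and "RF touchup'= 0 AND 'ABL >90 days' = 0". All three flags come from the core-lab Excel file. The Databases section of the SAP (numbered 2.3.1) lists the second as "Radiofrequency (RF) touchup" and gives no coding rule for any of the three.

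**The concern.** The non-study-device limb stops rescue by another device from being credited to the study system. A derivation that looks only for radiofrequency before day 90 is narrower than the definition it should implement. The limit on repeats in Protocol 3.11.3 serves a similar purpose, and no term in the SAP rule counts repeats.

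Both gaps can only move a subject from failure to success, so any error raises the reported rate. The off-drug rate is built from the same variable and would carry the error over. No hypothesis test is attached, but Protocol 5.3 says the results will be used to design further studies, so the estimate matters.

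**Working it through.** The plan states no figure for this point, so there is none to reproduce. The check compares the rules and then sizes the effect.

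**Step 1: the rules.**
- SAP 2.5: success = (status = 0) and (RF touchup = 0) and (ABL >90 days = 0).
- Protocol 6.4 alone: success = no arrhythmia after blanking, no study-device ablation after blanking, and no non-study ablation at any time.
- Protocol 6.4 with 3.11.3: as above, and fewer than two repeat ablations on or before day 90.

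Two readings are assumed. RF touchup is taken as RF at any time, because the composite labels in SAP 2.4.5 put a day-90 limit on cardioversion and ablation but none on RF. Status is taken as rhythm after blanking.

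**Step 2: eight scenarios, each with no other failure.**

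| Scenario | 6.4 alone | 6.4 with 3.11.3 | SAP 2.5 |
|---|---|---|---|
| No event | success | success | success |
| One study-device repeat by day 90 | success | success | success |
| RF non-study ablation by day 90 | failure | failure | failure |
| Non-RF non-study ablation by day 90 | failure | failure | **success** |
| Two study-device repeats by day 90 | success | failure | **success** |
| Non-RF non-study ablation after day 90 | failure | failure | failure |
| Study-device ablation after day 90 | failure | failure | failure |
| AF/AFL/AT after day 90 | failure | failure | failure |

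The SAP rule agrees with 6.4 alone in 7 of 8 scenarios and with 6.4 plus 3.11.3 in 6 of 8. The non-RF case is wrong under either reading. The two-repeat case is wrong only if 3.11.3 governs. Replacing the RF term with a test for any non-study device gives 8 of 8 against 6.4 alone. Adding a limit on repeats gives 8 of 8 against 6.4 with 3.11.3.

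**Step 3: can two repeats fit by day 90?** The remap window is 75 ± 15 days, so day 60 to day 90, wholly inside blanking. A subject reablated earlier for recurrence and touched up again at the remap would have two.

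**Step 4: size.** The shift in percentage points is 100 × k / N for k affected subjects.
- N = 40 (planned maximum): k = 1 gives 100 × 1/40 = 2.5; k = 2 gives 5.0.
- N = 25 (printed in the shells of SAP Tables 5 and 19): k = 1 gives 100 × 1/25 = 4.0; k = 2 gives 8.0. Table 13, which reports this endpoint, leaves N blank.

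As an illustration, assume 60% success at N = 40, with exact 95% intervals:
- as scored, 24/40 = 60.0% (43.3 to 75.1)
- one reclassified, 23/40 = 57.5% (40.9 to 73.0)
- two reclassified, 22/40 = 55.0% (38.5 to 70.7)

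The first interval is 75.1 − 43.3 = 31.8 points wide, so a shift of one or two subjects is small beside the sampling uncertainty, but it always goes the same way.

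**The case against.** **The second-repeat case is not a SAP coding error.** A reader might infer that the SAP overrides a settled protocol failure. The documents do not support that. Protocol 6.4(a) and the Executive Summary limit study-device failures to the period after blanking. Protocol 3.9 and the Executive Summary permit study-device reablation in blanking without giving a number. Only 3.11.3 adds the limit. SAP 2.4.6.2 copies 6.4, and for this limb the rule implements that text faithfully. The SAP also cites protocol Revision C, while the protocol supplied is Revision E; whether Revision C contained the 3.11.3 sentence cannot be checked. This objection stands, so the second case is a conflict inside the protocol that the SAP inherits.

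**The flags are undefined.** RF touchup could be shorthand for any non-study ablation, or the status flag could already absorb these failures. Nothing says so, and the SAP spells the field out as radiofrequency, but nothing excludes it. The finding must therefore be conditional on the rule as written.

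**The cases may never arise.** The core-lab file names only RF and PFA for ablation at the remap, which suggests RF was the non-study energy expected. Protocol 3.12.5 still admits any commercially approved device. A zero count would remove the effect on the result, but not the mismatch between definition and rule.

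**There are safeguards.** SAP Listing 12 will list additional ablations, and Protocol 9.10 has the committee adjudicate major outcomes. Both make a mis-scored subject easier to spot. Neither changes a rule computed from the Excel flags.

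**Conclusion.** The mismatch between SAP 2.5 and SAP 2.4.6.2 holds on the text. It does not depend on the protocol revision, because the SAP carries the non-study-device limb itself. It rests on reading RF touchup as its name says. The second-repeat question is open until the sponsor decides whether 6.4 or 3.11.3 governs.

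Three stronger readings are not supported:
- That the reported rate is inflated: no count of affected subjects is given.
- That rescue ablation in blanking escapes altogether: with the RF flag read as any time, RF rescue is caught, and later ablation with any device is caught by the day-90 flag.
- That an error rate or power is affected: the study tests no hypothesis.

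The effect is upward only, in whole-subject steps on a secondary descriptive proportion. Severity is minor to moderate.

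**What to change.** 1. In the SAP 2.5 rule, replace the RF touchup term with a requirement of no ablation for AF/AFL/AT with any non-study device, whatever the energy source, from the Index Procedure through assessment.
2. Reconcile Protocol 6.4 with 3.11.3, without sight of the success rate. If the 3.11.3 limit stands, add a condition of no more than one repeat ablation on or before day 90 to Protocol 6.4, SAP 2.4.6.2 and the SAP 2.5 rule. If it does not stand, remove it from 3.11.3. Either way, a single study-device repeat in blanking remains a non-failure.
3. Define the coding of the three Excel flags, and cite the current protocol revision in the SAP.
4. Derive the tests from the remap ablation fields in the core-lab file, the additional-ablation item on the remap form, the ablation history taken at each visit (Protocol Table 3) and the device lot or serial numbers recorded on the CRF (Protocol 2.5). Use the medical record (Protocol 10.2.1) as back-up, since the CRF entries may not identify every commercial device.
5. Leave the separate composites labelled as excluding RF unchanged.

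The cost is a few lines of SAP text, a short protocol clarification, one or two derived tests, and a record check confined to subjects with any ablation after the Index Procedure or a non-study ablation during it. The reported success rate may fall slightly.

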2.5. Derived Criteria Calculation

If at least one of the items needed to calculate a derived criteria is missing, then the corresponding derived criteria will be considered as missing.

Patient Disposition:

- Derived criteria “Enrolled population” will be analysed as:
IF the date of patient consent is filled in **Patient eligibility form (IE)** **THEN** “Enrolled population” = ‘Yes’
ELSE “Enrolled population” = ‘No’.
- Derived criteria “ITT population” will be defined as follows:
IF “Enrolled population” = ‘Yes’ in **Patient eligibility form (IE)** and the date of the Procedure is filled in **Procedural data form (PR)** **THEN** “ITT population” = ‘Yes’
ELSE “ITT population” = ‘No’.
- Derived criteria “Per Protocol population PP” will be defined as follows:
IF “ITT population” = ‘Yes’ **AND** Device Deficiency Number is not filled **AND** Serial # is not filled in **Device Deficiency DD Form** **THEN** Per Protocol population = ‘Yes’
ELSE Per Protocol population = ‘No’.
- Derived criteria “Time of patient follow-up” will be calculated as:
Date of study exit/withdrawal (*) in **Patient eligibility form (IE)** – date of procedure in **Procedural data form (PR)**
*if the patient is still in the study, the last visit date will be used instead of the exit/ withdrawal one.
- Derived criteria “COVID status” will be calculated as:
IF “Related to COVID-19 situation” =1 **OR** the term “COVID” exist in “reason for deviation” **AND** date of deviation is filled in **Protocol deviation form (PD)**, **THEN** CLASS=“ COVID-19”
ELSE IF date of deviation is filled **THEN** CLASS= “NOT COVID-19”.

Baseline Patient Characteristics:

- Derived criteria “Time from first AF diagnosis until consent date (months)” will be defined as follows:
Informed consent date – date of first documented AF diagnosis in **AF history form (AH)**.
- Derived criteria “Time between the most recent AF episode and the enrollment (months)” will be defined as follows:
Informed consent date – date of most recent AF episode in **AF history form (AH)**.
- Derived criteria “Permanent pacemaker or ICD” will be defined as follows:
IF Pacemaker, Implantable Cardioverter Defibrillator or Cardiac Resynchronization therapy device= ‘Yes’ in **Patient eligibility Form (IE)** **THEN** Permanent pacemaker or ICD=‘Yes’

CONFIDENTIEL / CONFIDENTIAL

Toute reproduction ou distribution, totale ou partielle, de ce document, sans autorisation préalable de ICON PLC est interdite.

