ELSE Freedom from AF/AFL/AT ='No'

- Derived criteria "Freedom from AF/AFL/AT with Class I/III AAD >90 days" will be defined as follows:

IF AF/AFL/AT status =0 **AND** Class I/III AAD >90 days =1 in **MDT excel file** **THEN** Freedom from AF/AFL/AT with Class I/III AAD >90 days ='Yes'

ELSE Freedom from AF/AFL/AT with Class I/III AAD >90 days ='No'

- Derived criteria "Freedom from AF/AFL/AT without Class I/III AAD >90 days" will be defined as follows:

IF AF/AFL/AT status =0 **AND** Class I/III AAD >90 days =0 in **MDT excel file** **THEN** Freedom from AF/AFL/AT without Class I/III AAD >90 days ='Yes'

ELSE Freedom from AF/AFL/AT without Class I/III AAD >90 days ='No'

- Derived criteria "Freedom from AF" will be defined as follows:

IF AF status =0 in **MDT excel file** **THEN** Freedom from AF ='Yes'

ELSE Freedom from AF ='No'

- Derived criteria "Freedom from AF with Class I/III AAD >90 days" will be defined as follows:

IF AF status =0 **AND** Class I/III AAD >90 days =1 in **MDT excel file** **THEN** Freedom from AF with Class I/III AAD >90 days ='Yes'

ELSE Freedom from AF with Class I/III AAD >90 days ='No'

- Derived criteria "Freedom from AF without Class I/III AAD >90 days" will be defined as follows:

IF AF status =0 **AND** Class I/III AAD >90 days =0 in **MDT excel file** **THEN** Freedom from AF without Class I/III AAD >90 days ='Yes'

ELSE Freedom from AF without Class I/III AAD >90 days ='No'

- Derived criteria "Freedom from AF/AFL/AT, no DCCV>90 days, no RF, no ablation >90 days" will be defined as follows:

CONFIDENTIEL / CONFIDENTIAL

Toute reproduction ou distribution, totale ou partielle, de ce document, sans autorisation préalable de ICON PLC est interdite.
Reproduction and distribution of this document, in whole or in part, is strictly forbidden without prior authorization from ICON PLC.

	STATISTICAL ANALYSIS PLAN	FARAPULSE PersAFOne SAP V1.0 PERSAFONE Page 23 /49
---	----------------------------------	--

IF AF/AFL/AT status =0 **AND** DCCV90D=0 **AND** RF touch up=0 **AND** ABL>90 day=0 in **MDT excel file** **THEN** Freedom from AF/AFL/AT, no DCCV>90 days, no RF, no ablation >90 days ='Yes'

ELSE Freedom from AF/AFL/AT, no DCCV>90 days, no RF, no ablation >90 days ='No'

- Derived criteria "Freedom from AF/AFL/AT, no DCCV>90 days, no RF, no ablation >90 days with Class I/III AAD >90 days" will be defined as follows:

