4.1.13. Table 13. Secondary Feasibility Endpoints

	ITT Population	
	N = XX	[95% CI]
Chronic Procedural Success (CPS)* for subjects who undergo the protocol-specified 75-Day Remapping Procedure	XX/XX (XX.X%)	[XX% - XX%]
Acute Cavotricuspid isthmus (CTI) Success**	XX/XX (XX.X%)	[XX% - XX%]
Therapeutic Success***	XX/XX (XX.X%)	[XX% - XX%]
On AADs	XX/XX (XX.X%)	[XX% - XX%]
Off AADs	XX/XX (XX.X%)	[XX% - XX%]
Durability of the CTI and/or other extra PV lesion set(s)	XX/XX (XX.X%)	[XX% - XX%]

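### Therapeutic Success on antiarrhythmic drugs is coded 'No' in both branches, so the On-AADs row of Table 13 can never exceed 0%

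*SAP*

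**What the plan says.** SAP 2.5 first derives overall Therapeutic Success from three flags in the sponsor's Excel file. It is 'Yes' when "AF/AFL/AT status'= 0 AND 'RF touchup'= 0 AND 'ABL >90 days' = 0", and 'No' otherwise. It then splits the result by the flag for Class I/III drug use after day 90.

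- **Off drug:** success gives 'YES' and failure gives 'NO'.
- **On drug, success:** "Therapeutic success ='Yes' AND Class I/III AAD>90days=1 in MDT excel file THEN therapeutic success On ADD ='No".
- **On drug, failure:** "Therapeutic success ='No' AND Class I/III AAD>90days=1 in MDT excel file THEN THEN therapeutic success On ADD ='No".

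The parallel on-drug rule for freedom from arrhythmia, earlier in the same section, does return a positive value: "Freedom from AF/AFL/AT with Class I/III AAD >90 days ='Yes".

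SAP Table 13 prints "Therapeutic Success" with an overall row, an On-AADs row and an Off-AADs row. On timing, SAP 2.4.6.2 says: "Therapeutic Success will be assessed from the end of the 90 Day Blanking Period through Months 6 and 12".

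**The concern.** A rule that gives the same answer for success and failure carries no information. A programmer who follows the SAP reports 0% success on drug. One who corrects the rule silently departs from the plan without a record.

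The on/off split is a prespecified result in both documents. Protocol 5.3 and SAP 2.2 say the results will be used to design further studies, so a false 0% on drug could be carried forward.

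The same block of derivations has four smaller weaknesses:

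- **(a) Time.** The success rule has no time condition, although results are required at two time points. Neither document says how the arrhythmia status flag is coded for a subject who leaves early.
- **(b) Table 7 on/off rows.** The freedom rules send everyone in the other drug group to 'No', while SAP 2.4.5 describes results within each drug group. Also, the last of these rules (freedom from AF, off drug, with the cardioversion, RF and ablation conditions) stores its result under the AF/AFL/AT name.
- **(c) Time to Therapeutic Failure.** Table 11 summarises it by mean, SD and median, whereas SAP 2.1.4 says time-to-event variables are described by Kaplan-Meier.
- **(d) Definition of failure.** Protocol 3.11.3 counts a second repeat ablation in the Blanking Period as a Therapeutic Failure. The endpoint definition in protocol 6.4 and SAP 2.4.6.2 does not. The criterion for nonstudy devices at any time is coded only through an RF touch-up flag and a flag for ablation after day 90.

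**Working it through.** The documents give no figure to reproduce. The study has no hypothesis test and no sample-size calculation.

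**Enumeration.** The inputs are four 0/1 flags from SAP 2.5: arrhythmia status, RF touch-up, ablation after day 90, and Class I/III drug after day 90. That gives 2 × 2 × 2 × 2 = 16 combinations.

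- Eight have the drug flag at 1. One of these (0, 0, 0 with drug = 1) is an overall success. The on-drug variable is 'No' in all eight.
- Eight have the drug flag at 0. The on-drug variable is never assigned, so they drop from the denominator under the non-missing rule in SAP 2.1.3.

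The row is therefore 0/n_on. With the first branch set to 'Yes', it becomes successes on drug divided by subjects on drug.

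**Illustration.** The documents give no split or rates. Assume 40 subjects (the protocol maximum), 30 off and 10 on drug, with 70% success in each group.

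| Table 13 row | As written | Corrected |
|---|---|---|
| Overall | 28/40 = 70% | 28/40 = 70% |
| Off AADs | 21/30 = 70% | 21/30 = 70% |
| On AADs | 0/10 = 0% | 7/10 = 70% |
| On + Off successes | 21 | 28 |

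**Intervals.** SAP 2.1.4 uses Agresti-Coull when a proportion is 0% and the asymptotic assumptions fail. With z² = 3.8415 and n = 10:

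- adjusted n = 10 + 3.8415 = 13.8415
- adjusted p = (0 + 1.9207)/13.8415 = 0.1388
- half-width = 1.96 × √(0.1388 × 0.8612/13.8415) = 0.182
- upper limit = 0.1388 + 0.182 = 0.321, lower limit truncated at 0

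So 0/10 prints as 0 to 32.1%. The exact interval for the correct 7/10 is 34.8 to 93.3%. The same formula gives 0 to 48.9% for 0/5 and 0 to 23.9% for 0/15.

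**Range.** With 5 to 15 subjects on drug and 60% success, 5 × 0.6 = 3 to 15 × 0.6 = 9 successes vanish from the split.

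**Item (a), early exits.** The size depends on how status is coded for them. If it is left blank, the rule "If at least one of the items needed to calculate a derived criteria is missing" makes the result missing. If it is 0, the subject counts as a success. For the second case, take N = 40, d failures and k exits, all before the first failure. The crude rate is 1 − d/40 and Kaplan-Meier gives 1 − d/(40 − k).

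| d | Crude | KM, k = 2 / 4 / 6 | Excess, points |
|---|---|---|---|
| 8 | 80.0% | 78.9 / 77.8 / 76.5% | 1.1 / 2.2 / 3.5 |
| 16 | 60.0% | 57.9 / 55.6 / 52.9% | 2.1 / 4.4 / 7.1 |

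This is an upper bound. The excess is zero if every exit follows the last failure.

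**Item (b), same split, taking 70% as free from arrhythmia.** The Table 7 rows read 21/40 = 52.5% off drug and 7/40 = 17.5% on drug, against 70% within each group. They sum to 28/40, so they are valid only as joint proportions (free and on drug, free and off drug). In the misnamed rule, literal execution overwrites the AF/AFL/AT off-drug variable and leaves the AF off-drug variable unassigned.

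**The case against.** The strongest reply is that this is an obvious typing slip with limited reach. It touches one sub-row of a secondary, descriptive endpoint. The intent is clear from the off-drug rule and the parallel on-drug rules. The error would also show itself, because the strata would not sum to the overall count. All of that stands, and it limits the consequence. It does not remove the need for a correction, because nothing elsewhere supplies the missing number. Table 7's plain freedom rows omit the RF and ablation conditions, and its composite rows and Graph 6 add cardioversion, which Therapeutic Success does not include.

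The size of the illustration is fairly questioned. The on-drug group may be small: protocol 3.11.3 expects drugs to be stopped towards the end of blanking unless the investigator objects, and exclusion 14 bars amiodarone after the index day. Two SAP table shells print N = 25 rather than 40. The separation of intervals is also specific to 7/10. At 60% success, the exact intervals for 3/5 (14.7 to 94.7%) and 6/10 (26.2 to 87.8%) overlap those printed for 0/5 and 0/10; only 9/15 (32.3 to 83.7%) does not. If no subject on drug succeeds, 0% is correct.

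On the smaller items:

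- The time condition in (a) might sit in the sponsor's data cut, which cannot be seen. SAP 2.1.4 already promises Kaplan-Meier rates at 180 and 365 days.
- The Table 7 rows in (b) are partly a matter of labelling.
- The device gap in (d) is hypothetical, since the listed remap field names only RF and PFA. Protocol 3.12.5 nevertheless treats any commercial ablation device used at remap as a failure.

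**Conclusion.** The point holds. As written, the On-AADs row of Table 13 is 0/n_on whatever the outcomes, or not estimable if nobody is on drug. It is wrong whenever at least one subject on drug succeeds. That follows from the text alone and needs no assumption. The number of successes lost does rest on assumption: 3 to 9 for 5 to 15 subjects on drug at 60% success.

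Overall Therapeutic Success, the off-drug row and the primary endpoints are not affected. The correction is still necessary, because a result required by both documents cannot be produced from the specification.

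Among the smaller items, the misnamed variable, the Table 11 mismatch and the conflict between protocol 3.11.3 and 6.4 are visible in the text. The early-exit bias is conditional on how the status flag is coded.

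**What to change.** Change the result of the first on-drug branch in SAP 2.5 to 'Yes', in a documented revision. This is one word, needs no new data and costs nothing. In the same revision:

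- **(a)** State how status is coded for subjects who exit early. Derive success separately at day 180 and day 365, either by Kaplan-Meier or as n/N among subjects who failed or were followed through the visit window. The Excel file described in SAP 2.3.1 (Databases) gives event days only for AF and for the combined arrhythmias ("AF/AFL/AT km (days"), with flags alone for RF touch-up and late ablation. Ablation dates must therefore come from the eCRF.
- **(b)** Restrict the Table 7 on/off rows to subjects in that drug group, or label them as joint proportions of all ITT subjects. Correct the variable name in the last freedom rule.
- **(c)** Report Time to Therapeutic Failure by Kaplan-Meier, in line with SAP 2.1.4.
- **(d)** Reconcile protocol 3.11.3 with the endpoint definition in protocol 6.4 and SAP 2.4.6.2, then code the agreed definition. Make the nonstudy-device criterion cover any nonstudy device, as that definition already states.

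Items (a) to (d) need minor programming, provided the eCRF holds the dates and device types; its forms are not shown in the documents. The stated success rate may come out slightly lower.
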